#### 9.4.1 *Clinical Safety Laboratory Assessments*

Investigators must document their review of each laboratory safety report. A central laboratory will perform the analyses and will provide reference ranges for these tests, except as noted below.

Hematology, serum chemistry, and urinalysis assessments are listed in Table 8.

**Table 8: Hematology, Chemistry, and Urinalysis Assessments**

Hematology			
• CBC with differential	• RBC	• MCH concentration	
• PT	• WBC (absolute)	• Red cell distribution width	
• PTT	• Hemoglobin	• Platelet count	
• INR	• Hematocrit		
	• MCV		
Blood Chemistry			
• AST	• Creatine kinase	• Sodium	
• ALT	• BUN	• Potassium	
• Total bilirubin	• Uric acid	• Chloride	

**Table 8: Hematology, Chemistry, and Urinalysis Assessments**

• Direct bilirubin	• Glucose	• Carbon dioxide
• ALP	• PTH	• Calcium
• LDH	• Total protein	• Phosphorus
• GGT	• Albumin	• GFR a
• Creatinine		
Urinalysis		
• pH	• Ketones	• Urine protein, total (quantitative) for urine protein to creatinine ratio
• Specific gravity	• Leukocyte esterase	• Urinary albumin to urinary creatinine ratio
• Protein (quantitative)	• Nitrite	
• Albumin (quantitative)	• Creatinine	
• Glucose	• Microscopic examination (only to follow-up abnormal findings)	
Metabolic Panel ( $\geq$ 10 hours fast)		
• Lipid panel (triglycerides, total cholesterol, LDL, HDL)		
Other Analyses		
• FSH b	• HbA1c	• Pregnancy test (WOCBP only; can be performed locally)
• AFP	• Insulin	• Serology/viral load ( APPENDIX 7 )
		• HIV testing must be performed where mandated by local requirements ( APPENDIX 8 ), and the test will be performed at a local lab

AFP = alpha-fetoprotein; ALP = alkaline phosphatase; ALT = alanine aminotransferase; AST = aspartate aminotransferase; BUN = blood urea nitrogen; CBC = complete blood count; FSH = follicle-stimulating hormone; GFR = glomerular filtration rate; GGT = gamma-glutamyl transferase; HbA1c = hemoglobin A1c; HDL = high-density lipoprotein; HIV = human immunodeficiency virus; INR = international normalized ratio; LDH = lactate dehydrogenase; LDL = low-density lipoprotein; MCH = mean corpuscular hemoglobin; MCV = mean corpuscular volume; PT = prothrombin time; PTH = parathyroid hormone; PTT = partial thromboplastin time; RBC = red blood cell; WBC = white blood cell; WOCBP = women of childbearing potential

a Estimated GFR, as calculated by the Modification of Diet in Renal Disease equation 

b FSH performed only in female participants  $<$  55 years to confirm menopause ([APPENDIX 4](#))

#### 9.4.2 Vital Signs

Refer to SOA in [Section 2](#) for timing of vital signs assessments.

#### 9.4.3 Physical Examinations

Schedules for physical examinations are provided in the SOA ([Section 2](#)). Complete and/or abbreviated physical examinations may be performed by a Doctor of Medicine (MD) or equivalent,

or someone who is authorized to perform the examinations by training and has been delegated this task by the principal investigator.

A physical exam for signs of [REDACTED], including skin and oral mucosa changes and hepatomegaly, will be performed at visits listed in the SOA ([Section 2](#)).

A full examination will include general appearance, skin, head, eyes, ears, nose, throat, neck, thyroid, chest/lungs, heart, abdomen, lymph nodes, and extremities. If the screening full physical examination is performed within 24 hours prior to dosing on Day 1, then a single exam may count as both the screening and Day 1 (abbreviated) physical examination.

Abbreviated physical exams will include an abdominal exam, assessments of ascites and hepatic encephalopathy, and symptom-focused assessments. An abbreviated examination may note any changes in the participant's condition (body systems) since the last assessment and does not preclude examination of any of the other body systems as clinically indicated. Every effort should be made to ensure the same evaluator will complete the examination for each participant at all visits throughout the study. Documentation of who performed the examination is to be recorded in source notes.

#### **9.4.4      *Electrocardiograms***

Refer to SOA in [Section 2](#) for timing of ECGs.

#### **9.4.5      *Imaging Safety Assessment – DXA Scan***

DXA scan (hip [including femoral neck] and lumbar spine) will be performed at the time points indicated in the SOA ([Section 2](#)).

Image acquisition guidelines and submission processes will be outlined in the site imaging manual, to be provided by the central imaging vendor. The sites will be trained and qualified in imaging procedures prior to scanning the first study participant. All images will be submitted to the central imaging vendor for assessment of the BMD.

Adequacy of DXA scan must be determined by the central imaging vendor prior to Randomization. The site will be informed of quality issues or the need to repeat scanning from the central imaging vendor. Note that at least 1 of the requested anatomic sites (hip [including femoral neck] or lumbar spine) must be evaluable for participants to be eligible for the study (See [Section 6.2](#)).

[figure not shown]
Any local incidental imaging findings of potential clinical relevance that are not directly associated with the objectives of the protocol should be evaluated and handled by the study investigator as per standard medical/clinical judgment.

[REDACTED]

[REDACTED]

[figure not shown]
[REDACTED]

[figure not shown]
[REDACTED]

[figure not shown]
#### 9.5 PK [REDACTED] Sampling Schedule for BMS-986263

Blood for PK samples will be drawn according to the sampling schedule shown in [REDACTED]. Blood for PK samples drawn on dosing days is strongly recommended to be taken from the contralateral arm to the IV drug administration. Information on the collecting, processing, and submission of samples to the central laboratory are in the reference manual(s).

[figure not shown]

A series of horizontal black bars of varying lengths and positions on a white background. The bars are irregular in shape, with some having sharp ends and others being more rounded. They are positioned at different heights and widths across the frame, creating a sense of depth and movement. The overall effect is abstract and minimalist.

## **10 STATISTICAL CONSIDERATIONS**

### **10.1 Sample Size Determination**

In this study, approximately 270 participants will be randomized via IRT in a 1:1:1 ratio to receive 45 mg BMS-986263 QW, 90 mg BMS-986263 QW, or placebo QW by IV infusion in a double-blind manner. The primary endpoint is the proportion of participants with  $\geq 1$  stage improvement in liver fibrosis (NASH CRN Fibrosis Score) as determined by liver biopsy after 12 weeks of treatment.

Assuming a Chi-Square test with an  $\alpha = 0.05$  and expected response rates for BMS-986263 90 mg, BMS-986263 45 mg, and placebo of 45%, 40%, and 20%, respectively, approximately 85 evaluable participants per treatment group in this study will have at least 80% power to detect superiority over placebo versus each dose, assuming a minimum difference of 20% from placebo. Accounting for a 6% dropout rate, approximately 90 participants will be randomized per treatment group.

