#### Study Treatment:

Study Drug for IM025017		
Medication	Potency	IP/Non-IP
BMS-986263 for injection	10 mg per vial; 3 mg/mL after reconstitution	IP
Placebo a for BMS-986263 for injection/on-site compounded sterile dosage form	NA	IP

IP = investigational product; IV = intravenous; NA = not applicable

a [REDACTED]

**Statistical Methods:** Efficacy analyses will be performed using the modified intent-to-treat population. Participants who discontinue early and do not have an Early Treatment Termination liver biopsy or otherwise have the result from the liver biopsy missing will be considered a “nonresponder” for the evaluation of the primary endpoint and other binary endpoints based on liver biopsy.

**Primary Endpoint Analysis:** To evaluate the effect of BMS-986263 (90 mg QW and 45 mg QW) on NASH CRN Fibrosis Stage at Week 12, a 95.0% confidence interval of response rate for active treatment versus placebo will be used to estimate the difference between the proportions of participants with  $\geq 1$  stage improvement in fibrosis on liver biopsy. Additionally, the odds ratio will be used to estimate improvement of treatment as compared with placebo for the proportion of participants with  $\geq 1$  stage improvement in fibrosis on biopsy at Week 12. A logistic regression will be performed with platelet count as independent covariate and stratified by the Randomization strata with a Z-test statistic at a two-sided significance level of  $\alpha=0.05$  to assess the difference of response rate separately between each BMS-986263 treatment group and placebo. To control for the family-wise (two-sided) Type I error rate of  $\alpha=0.05$ , the statistical tests will be performed in the following hierarchical order: 1) BMS-986263 90 mg versus placebo, and 2) BMS-986263 45 mg versus placebo. If the first comparison is not statistically significant, then the second comparison will be treated as descriptive in nature.

**Secondary [REDACTED] Endpoint Analyses:** No adjustment will be made for multiplicity for secondary [REDACTED] endpoints. Secondary [REDACTED] endpoints will be analyzed in a similar method as the primary endpoint unless otherwise specified in the statistical analysis plan (SAP).

[figure not shown]

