Vital signs	X		X	X	X	X	X	X		X	X	X	X	X	X	X	Includes body temperature, respiratory rate, blood pressure, and heart rate. Blood pressure and heart rate should be measured after the participant has been resting quietly for at least 5 minutes.
12-lead ECG														X	X		ECG should be performed after the participant has been supine for at least 5 minutes.
Adverse events	X	X	X	X	X	X	X	X	X	X	X	X	X	X	X	X	Nonserious AEs must be collected from the time of the first dose of the study treatment through the date of the follow-up or last visit. Monitoring for AEs

**Table 2:** Treatment Period Procedural Outline

Procedure/ Visit Day (± 3 days for all visits unless otherwise noted)	D 1	D 4	D 8	D 15	D 22	D 29	D 36	D 43	D 46 a	D 50	D 57	D 64	D 71	D 78	D 85	ETT	Notes	
	R	W 1	W 2	W 3	W 4	W 5	W 6		W 7	W 8	W 9	W 10	W 11	W 12				
																	will occur at every study visit. (See Section 9.2 ).	
Serious adverse events	X	X	X	X	X	X	X	X	X	X	X	X	X	X	X	X	All SAEs must be collected from the date of participant's written consent until 30 days post discontinuation of dosing or participant's participation in the study if the last scheduled visit occurs at a later time (last visit for participation). See Section 9.2 .	
Clinical Efficacy Assessments																		
Liver biopsy																X	X	Liver biopsy should be performed within ± 3 days of visit window. Four additional days are allowed under extenuating circumstances with Medical Monitor approval. In case of early termination of treatment, to be obtained at ETT visit only if the participant has completed at least the Week 6 visit. See Section 9.1.2 .

**Table 2:** Treatment Period Procedural Outline

Procedure/ Visit Day (± 3 days for all visits unless otherwise noted)	D 1	D 4	D 8	D 15	D 22	D 29	D 36	D 43	D 46 a	D 50	D 57	D 64	D 71	D 78	D 85	ETT	Notes
	R		W 1	W 2	W 3	W 4	W 5	W 6		W 7	W 8	W 9	W 10	W 11	W 12		

**Table 2:** Treatment Period Procedural Outline

Procedure/ Visit Day (± 3 days for all visits unless otherwise noted)	D 1	D 4	D 8	D 15	D 22	D 29	D 36	D 43	D 46 a	D 50	D 57	D 64	D 71	D 78	D 85	ETT	Notes	
	R		W 1	W 2	W 3	W 4	W 5	W 6		W 7	W 8	W 9	W 10	W 11	W 12			
Laboratory Assessments																		

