### **10.2 Populations for Analyses**

The following populations are defined for analysis purposes:

Population	Description
Enrolled	All participants who sign informed consent.
Randomized	All participants who are randomized to a treatment, analyzed as per randomized treatment.
Modified intent-to-treat (mITT)	All participants who are randomized to a treatment and receive at least 1 dose of study medication analyzed as per randomized treatment. All primary efficacy analyses will be conducted using this population.
PK	All participants who receive at least 1 dose of BMS-986263 and have any available concentration-time data.
Safety (As-treated)	All randomized participants who receive at least 1 dose of study treatment, analyzed according to the treatment actually received. All safety analyses will be conducted using this population.

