### 10.4.1 Efficacy Analyses

Efficacy analyses will be performed using the mITT population. Participants who discontinue early and do not have an ETT liver biopsy or otherwise have the result from the liver biopsy missing will be considered a “nonresponder” for the evaluation of the primary endpoint and other binary endpoints based on liver biopsy.

**Primary Endpoint:** To evaluate the effect of BMS-986263 (90 mg QW and 45 mg QW) on NASH CRN Fibrosis Stage at Week 12, a 95.0% confidence interval (CI) of response rate for treatment versus placebo will be used to estimate the difference between the proportions of participants with  $\geq 1$  stage improvement in fibrosis on liver biopsy. Additionally, the odds ratio will be used to estimate improvement of treatment as compared with placebo for the proportion of participants with  $\geq 1$  stage improvement in fibrosis on biopsy at Week 12. A logistic regression will be performed with platelet count as continuous independent covariate and stratified by the Randomization strata with a Z-test statistic at a two-sided significance level of  $\alpha=0.05$  to assess the difference in distribution of response rate separately between each BMS-986263 treatment group and placebo. To control for the family-wise (two-sided) Type I error rate of  $\alpha=0.05$ , the statistical tests will be performed in the following hierarchical order: 1) BMS-986263 90 mg versus placebo, and 2) BMS-986263 45 mg versus placebo. If the first comparison is not statistically significant, then the second comparison will be treated as descriptive in nature.

**Secondary [REDACTED] Endpoints:** No adjustment will be made for multiplicity for secondary [REDACTED] endpoints. Secondary [REDACTED] endpoints will be analyzed in a similar method as the primary endpoint unless otherwise specified in the SAP.

Selected continuous endpoints will be characterized using descriptive statistics and may be analyzed by analysis of covariance methods and/or by a mixed model for repeated measurements. Treatment differences at prespecified time points will be estimated using least squares means. Full details regarding this model and covariance structure will be provided in the SAP.

Categorical endpoints will be summarized using counts and percentages and when appropriate, may be analyzed using categorical analysis methods.

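### Does the 80% power statement in Section 10.1 overstate the chance of a confirmatory claim for 45 mg, given that 45 mg is tested only after 90 mg succeeds?

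*Combined protocol and SAP*

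**What the plan says.** Section 10.1 of the protocol sizes the trial with a chi-square test at α = 0.05, expected response rates of 45% (90 mg), 40% (45 mg) and 20% (placebo), and about 85 evaluable participants per group. It concludes that the study "will have at least 80% power to detect superiority over placebo versus each dose, assuming a minimum difference of 20% from placebo". The allowance for loss follows: "Accounting for a 6% dropout rate, approximately 90 participants will be randomized per treatment group". The synopsis (Number of Participants) carries the same power claim.

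The testing rule is in Section 10.4.1 and in the synopsis under Statistical Methods. To control the two-sided family-wise error rate at 0.05, "the statistical tests will be performed in the following hierarchical order": 90 mg against placebo, then 45 mg against placebo. Section 10.4.1 adds: "If the first comparison is not statistically significant, then the second comparison will be treated as descriptive in nature".

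Three other provisions affect how the sizing model relates to the final analysis:

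- The primary test is not the plain chi-square: "A logistic regression will be performed with platelet count as continuous independent covariate and stratified by the Randomization strata".
- The mITT population in Section 10.2 consists of those "randomized to a treatment and receive at least 1 dose of study medication analyzed as per randomized treatment", so participants who are never dosed drop out of the analysis.
- Under Section 10.4.1, participants who stop early and "do not have an ETT liver biopsy or otherwise have the result from the liver biopsy missing will be considered a" non-responder. In the Schedule of Activities (Table 2), the early-termination biopsy is "to be obtained at ETT visit only if the participant has completed at least the Week 6 visit", so dosed participants who stop sooner fall under this rule.

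**The concern.** Under a fixed testing sequence, the chance of a confirmatory claim for the second dose is the probability that both comparisons are significant. That can never exceed the power of the second comparison alone. Section 10.1 does not mention the sequence, does not call its 80% a per-comparison figure, and gives no joint probability. A reader could take the sentence as an 80% chance of a formal claim for each dose.

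The sentence also refers to a minimum difference of 20 points. If both doses only just reached that difference, the 45 mg claim would hang on a first test with power of about 82%, and the loss from the gate would be noticeable. Section 5.4 names choice of dose and regimen for later development among the aims, so an overstated chance of a 45 mg claim could mislead planning.

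A second doubt is what the 6% loss means. Undosed participants shrink the analysed group. Dosed participants without a biopsy result stay in and lower the response rates. Section 10.1 does not say which it assumes, or whether 45/40/20 already count missing biopsies as failures.

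**Working it through.** **Inputs.** Rates 45/40/20, chi-square, α = 0.05, 85 evaluable and 90 randomised per group (Section 10.1); two-sided testing and the 90-then-45 mg order (Section 10.4.1).

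**1. Reproduce the stated power.** For a pairwise pooled chi-square with n per group,

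power = Φ{ [(p₁ − p₀) − 1.96·√(2p̄(1 − p̄)/n)] / √[(p₀(1 − p₀) + p₁(1 − p₁))/n] }, where p̄ = (p₀ + p₁)/2.

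- 45 mg (0.40 v 0.20, p̄ = 0.30, n = 85): √(0.42/85) = 0.0703, times 1.96 = 0.1378; √(0.40/85) = 0.0686; (0.20 − 0.1378)/0.0686 = 0.907; power 81.8%.
- 90 mg (0.45 v 0.20, p̄ = 0.325, n = 85): √(0.43875/85) = 0.0718, times 1.96 = 0.1408; √(0.4075/85) = 0.0692; (0.25 − 0.1408)/0.0692 = 1.577; power 94.3%.

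Exact binomial enumeration of the uncorrected Pearson test gives 82.2% and 94.3%. Both exceed 80%, so the claim reproduces as per-comparison power. The loss allowance also fits: 90 × 0.94 = 84.6, about 85.

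**2. Power for 45 mg under the gate.** The two comparisons share the placebo arm and so are positively correlated. Conditioning on the placebo count x₀,

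P(both significant) = Σ P(x₀) · P(90 mg significant | x₀) · P(45 mg significant | x₀).

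All figures below are exact, count only results favouring active treatment, and are in percent:

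| Case | 90 mg alone | 45 mg alone | 45 mg under the gate |
|---|---|---|---|
| 85 analysed, 45/40/20 | 94.3 | 82.2 | 79.6 |
| 86 analysed, 45/40/20 | 94.6 | 82.7 | 80.2 |
| 90 analysed, 45/40/20 | 95.4 | 84.2 | 81.9 |
| 90 dosed, 6% imputed (rates × 0.94: 42.3/37.6/18.8) | 93.6 | 81.0 | 78.0 |
| 85 analysed, 40/40/20 | 82.2 | 82.2 | 71.8 |
| 90 dosed, 6% imputed, 40/40/20 × 0.94 | 81.0 | 81.0 | 70.0 |

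A simulation of 2 million trials with 85 per group gives 79.6% and 71.8% for the two planning cases.

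**3. Cost of the gate.** At the planned rates with 85 analysed it is 82.2 − 79.6 = 2.6 points. At 40/40/20 it is 82.2 − 71.8 = 10.4 points. With 85 per group, 45 mg at 40% and placebo at 20%, gated power for 90 mg rates of 40, 42, 44, 45 and 46% is 71.8, 75.9, 78.6, 79.6 and 80.3%.

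**4. The split of the losses.** With five lost per group (5/90 = 5.6%, close to the planned 6%), gated 45 mg power at 45/40/20 runs from 78.3% (all five imputed) to 79.6% (all five undosed). If the planning rates already count missing biopsies as failures, only undosed losses matter, and the range is 79.6% (five undosed) to 81.9% (none).

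**The case for a change.** The strongest case for a change is that no sentence in the plan gives the probability that matters for a formal 45 mg claim, and the wording on a minimum difference invites the reader to picture both doses at 20 points, where the gated figure falls to about 72%. Adding a label and one number would cost only a few words in two places. The facts in this are right: the label is absent, the joint figure is absent, and the loss assumptions are not spelled out.

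The inference that the plan needs correcting does not follow:

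- The sentence speaks of each dose against placebo, under a pairwise test with a rate given for each dose. Its natural reading is per comparison, and on that reading it is true. It stays true at 81.0% for 45 mg with 6% imputed.
- Both Section 10.1 and the synopsis put 90 mg at 45%. The 20-point minimum describes the smaller of the two planned differences, 40% against 20%. The 40/40/20 case is a sensitivity analysis, not the plan's assumption, and even there each pairwise power is 82.2% with 85 analysed.
- The sequence and its consequence for 45 mg are stated in both the synopsis and Section 10.4.1. Nothing in the plan promises 80% power for joint success.
- The split of losses moves the gated figure by 79.6 − 78.3 = 1.3 points, too little to affect the design.

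**Conclusion.** No change is needed. The stated power is correct per comparison: 94.3% for 90 mg and 82.2% for 45 mg with 85 per group. At the planned rates, power for a confirmatory 45 mg claim is about 80%: 79.6% with 85 analysed and none imputed, 78.0% with 90 dosed and 6% imputed. The shortfall from 80% is thus 0.4 to 2.0 points. One more evaluable participant per group (86) already gives 80.2%, and Section 10.1 says only approximately 85.

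The 70-72% range applies if 90 mg also has a true advantage of only 20 points. It is useful background for anyone planning around 45 mg, but it lies outside the stated assumptions. If the gate fails in this Phase 2 study, 45 mg is still estimated and reported, descriptively.

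These figures rest on the uncorrected chi-square named for sizing, equal loss across groups and independent binomial arms. They leave out the platelet and strata adjustment, which could raise power but cannot be sized from the documents, and the possible 30% futility look, whose rule is left to the DMC Charter and DMC SAP. Section 10.1 could add the words per comparison and a gated figure of about 80%, but that would only annotate a correct number. The sample size, the tests, the control of Type I error and the conclusions would all stay the same.

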### **10.2 Populations for Analyses**

The following populations are defined for analysis purposes:

Population	Description
Enrolled	All participants who sign informed consent.
Randomized	All participants who are randomized to a treatment, analyzed as per randomized treatment.
Modified intent-to-treat (mITT)	All participants who are randomized to a treatment and receive at least 1 dose of study medication analyzed as per randomized treatment. All primary efficacy analyses will be conducted using this population.
PK	All participants who receive at least 1 dose of BMS-986263 and have any available concentration-time data.
Safety (As-treated)	All randomized participants who receive at least 1 dose of study treatment, analyzed according to the treatment actually received. All safety analyses will be conducted using this population.

